9.2. Physician and Subject Independent Response to Continue to Current Treatment

The number and percentage of physician and subject independent response (Yes, No) to the question “Would you choose to continue current treatment?” at week 24 (Visit 8) and at week 48 (Visit 11) will be summarized by treatment group. The response rate of “Yes” between treatment groups will be tested using Pearson’s chi-square test (or Fisher’s exact test if any expected count is less than 5), for both physician and subject at week 24 (Visit 8) only. In the double-blind phase only, missing response will be imputed as “No”.

Physician and subject independent response to continue current treatment will be provided in a listing by study phase.

9.3. Pulmonary Function Tests

Descriptive statistics of observed and change from baseline will be presented for PFT results including DLCO % predicted and FVC % predicted at each scheduled visit during double-blind treatment phase and open-label extension phase, respectively. In addition, change from baseline of active treatment will be presented for open-label extension phase.

The treatment difference between Acthar and placebo for change from baseline to each visit in the double-blind treatment phase in DLCO % predicted and FVC % predicted will be evaluated using a two-sample T-test. Change in DLCO % predicted and FVC % predicted will be plotted in line graph over time showing the means and SEs by visit across both study phases.

Also, the treatment effect for the change from baseline to each scheduled visit in the double-blind treatment phase in DLCO % predicted and FVC % predicted will be estimated using a mixed effect model with repeated measures (MMRM) model. The MMRM model will use change from baseline as the response variable, and include visit, treatment group, and visit-by-treatment group interaction as covariates. Additionally, visit (categorical) will be specified as a repeated effect and unstructured (UN) correlation matrix will be used to model intra-subject correlation. In case a convergence issue will arise using the UN correlation matrix, (1) first-order autoregressive (AR1) or (2) Compound Symmetry (CS) will be used to enable model convergence (in this order). The least square (LS) mean difference with 95% CI and p-value will be presented.

In addition, improvement in DLCO % predicted and FVC % predicted will be explored by using criteria ($\geq 5\%$, $\geq 10\%$ and $\geq 15\%$, respectively). Number and percentage of subjects with improvement will be provided at each scheduled visit by double-blind treatment phase and open-label extension phase. Pearson's chi-square test (or Fisher's exact test if any expected count is less than 5) will be used to compare the treatment difference between treatment groups in the double-blind treatment phase. The following endpoints will be included:

- Percentage of subjects with improvement in DLCO % predicted of $\geq 5\%$
- Percentage of subjects with improvement in DLCO % predicted of $\geq 10\%$
- Percentage of subjects with improvement in DLCO % predicted of $\geq 15\%$
- Percentage of subjects with improvement in FVC % predicted of $\geq 5\%$
- Percentage of subjects with improvement in FVC % predicted of $\geq 10\%$
- Percentage of subjects with improvement in FVC % predicted of $\geq 15\%$

Percentage of subjects in each treatment group meeting each improvement criterion will be analyzed using both imputation and data as observed methods in double-blind treatment phase, and using data as observed method only in the open-label extension phase. For the analysis using imputation, mITT subjects without an evaluable assessment for the criterion will be considered as no improvement for that criterion. For the analysis of data as observed, mITT subjects without an evaluable assessment for the criterion will be excluded from the analysis for that criterion.

Other PFT assessments including FEV1, FVC, FEV1/FVC ratio, PEFR or FEF_{max}, TLC, RV, DLCO (uncorrected for Hb) and DLCO/VA if available will be summarized by using descriptive statistics for observed and change from baseline at the scheduled visits during double-blind treatment phase and open-label extension phase. The treatment difference between Acthar and placebo for change from baseline to each visit in the double-blind treatment phase will be evaluated using a two-sample T-test.

A listing will be provided for the PFT data by subject and visit.

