- Two baselines, baseline of overall study and baseline of active treatment, have been defined. Baseline of overall study is defined as the last assessment prior to the first dose of IMP at the double-blind treatment phase. Baseline of active treatment is defined as the last assessment prior to the first dose of active treatment in either the double-blind treatment phase or the open-label extension phase. All the analysis in the open-label extension phase that involves presenting change and/or percent change from baseline will present change/percent change from both baselines.
- Summary statistics will be provided for all study variables with descriptive statistics (number of subjects, mean, standard deviation (SD), median, minimum,

and maximum) for numerical (or continuous) variables. Frequency and percentages will be calculated for categorical variables.

- Unless specified otherwise for a given analysis, all statistical tests, when applicable, will be 2-sided with a significance level of 0.05.
- All data collected will be presented in listings, sorted by treatment group, subject identifier and date/time of procedure or event, if applicable.

All analyses will be conducted using SAS® Version 9.4 or higher. The Medical Dictionary for Regulatory Activities (MedDRA) version 23.0 will be used for coding adverse events (AEs), and medical and surgical histories. Prior or concomitant medication data will be coded according to the Anatomical Therapeutic Chemical (ATC) coding scheme of the World Health Organization (WHO) Drug Dictionary (Enhanced B2 dated March 2018 version, or higher) level 2 term.

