9.5. Patient-Reported Outcomes and Symptom Questionnaires

Descriptive statistics of observed, change from baseline and percentage change from baseline values will be provided at scheduled visits during double-blind treatment phase and open-label extension phase, respectively. Descriptive statistics of baseline of active treatment, change and percentage change from baseline of active treatment values at visits in open-label extension phase will be provided additionally. The change from baseline and percentage change from baseline values to each visit will be analyzed using similar statistical methodology for all patient-reported outcomes and symptom questionnaires unless specified otherwise at visits during double-blind treatment phase.

The patient-reported outcomes and symptom questionnaires will include the following:

- Total score of Steroid Toxicity Questionnaire where lower scores indicate better status.
- Scores of each of the 5 King's Sarcoidosis Questionnaire Modules (General Health Status, Lung, Medication, Skin, and Eyes) where higher scores indicate improvement.
- Total scores of each of the 4 King's Sarcoidosis Questionnaire overall scales (Lung Health Status [General Health Status module and Lung module], Skin Health Status [General Health Status module and Skin module], Eye Health Status [General Health Status module and Eye module], Lung-Skin Health Status [General Health Status module, Lung module and Skin module]) where higher scores indicate improvement and a change of 4 points is considered clinically meaningful.
- Total score of Fatigue Assessment Scale where lower scores indicate improvement and a change of 4 points is considered clinically meaningful.
- Patient's Global Assessment where higher scores indicate better status.
- Physician Global Assessment where higher scores indicate better status.
- Medical Research Council Dyspnea Scale where lower scores indicate better status.
- Total score and each score of the 3 domains (Physical, Psychological and Social) of Leicester Cough Questionnaire where higher scores indicate better health status.
- Work Productivity and Activity Impairment (WPAI)

Calculation for above scores are provided in Appendix 15.2.

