The treatment difference between Acthar and placebo for both change from baseline and percentage change from baseline to visits in the double-blind treatment phase in each outcome or questionnaire score will be evaluated using a two-sample T-test. Wilcoxon rank sum test may be used if the data are not normally distributed. Percentage change in King's Sarcoidosis Questionnaire and Fatigue Assessment Scale will be plotted in line graph over time showing the means and SEs. For WPAI data, only a listing will be provided.

If result is missing at a post-baseline visit, the missing result will be imputed using the LOCF method. No imputation will be applied to the open-label extension phase. All

summaries and analyses will be conducted on both the observed values and the LOCF values.

Listings will be provided for each patient-reported outcome and symptom questionnaire by subject and visit.

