11.2. Genetic Profile

Genetic sample obtained for subjects who has signed the genetic inform consent form at study entry may be explored and presented in tables. Descriptive statistics will be provided if data is available.

All genetic data will be presented in a listing.

12. Interim Analysis

No formal interim analysis is planned.

13. Changes in the Planned Analysis

The summary of changes presented below reflects the changes in the planned analysis described in protocol:

- The protocol planned endpoint analysis for “Change from baseline in WPAI over time” will not be performed given very few subjects have taken WPAI questionnaire. WPAI data will be only presented in listings.
- The protocol planned endpoint analysis for “Time to response (TTR) as evaluated at earlier time points (Weeks 4 to 20) as determined by the investigator based on clinical judgment” will not be performed.
- The protocol planned analysis for biomarker and genetic endpoints may not be performed depending on the availability of the data.

14. References

Judson MA. Advances in the diagnosis and treatment of sarcoidosis. *F1000Prime Reports* 2014; 6: 89.

Mallinckrodt ARD, Inc. A Phase 4 Multicenter, Randomized, Double Blind, Placebo Controlled Pilot Study to Assess the Efficacy and Safety of H.P. Acthar® Gel in Subjects with Pulmonary Sarcoidosis. Original, 06 October 2017.

15.Appendices

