15.4. SAS Procedures

- T test

```
ods output ttests=ttest;
proc ttest data=xxx sides=2 alpha=0.05 h0=0;
  class TRT;
  var AnalVar;
run;
```

- Pearson's chi-square test

```
proc freq data=xxx;
  tables TRT*AnalVar /chisq;
  output out=chisq pchi;
run;
```

- Fisher's exact test

```
proc freq data=xxx;
  tables TRT*AnalVar / fisher;
  output out= fisher exact;
run;
```

- MMRM

```
ods output lsmeans=lsm diffs=diff;
proc mixed data=xxx;
  class TRT AVISITN USUBJID;
  model AnalVar = BASVAR TRT AVISITN TRT*AVISITN;
  repeated AVISITN / type=UN subject=USUBJID;
  lsmeans TRT*AVISITN / diff cl;
run;
```

Statistical Analysis Plan (SAP) Client Approval Form

Client:	Mallinckrodt ARD, LLC
Protocol Number:	MNK14344100
Document Description:	Final Statistical Analysis Plan
SAP Title:	A Multicenter, Randomized, Double Blind, Placebo Controlled Exploratory Study to Assess the Efficacy and Safety of Acthar® Gel in Subjects with Pulmonary Sarcoidosis
SAP Version Number:	3.0
Effective Date:	02FEB2022

Author(s):

For PPD: [REDACTED], [REDACTED] [REDACTED]
[REDACTED]
I approve this document
02 Feb 2022 11:21:10 -05:00
DocuSign

Approved by:

[REDACTED]
[REDACTED]
[REDACTED]
02-Feb-2022
Date (DD-MMM-YYYY)
Mallinckrodt ARD, LLC

[REDACTED]
[REDACTED]
Date (DD-MMM-YYYY)
Mallinckrodt ARD, LLC

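### The MMRM for change in FVC and DLCO % predicted has no baseline term in the SAP 9.3 text but has one (BASVAR) in the Appendix 15.4 code

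*SAP*

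**What the plan says.** SAP 9.3 plans two comparisons of change from baseline in FVC and DLCO % predicted during the double-blind phase: a two-sample t-test at each visit and, in addition, an MMRM. The MMRM has change from baseline as response, "and include visit, treatment group, and visit-by-treatment group interaction as covariates". Visit is the repeated effect and the covariance is unstructured, with AR(1) and then compound symmetry as fallbacks. An LS mean difference, 95% CI and p-value are to be presented. No baseline covariate is named.

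SAP Appendix 15.4 gives the SAS code under the label MMRM. Its model statement is "model AnalVar = BASVAR TRT AVISITN TRT*AVISITN". BASVAR does not appear in the CLASS statement, so it is fitted as a continuous covariate. The SAP does not define it.

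SAP 4.3 sets the baseline for the double-blind phase: "Baseline of overall study is defined as the last assessment prior to the first dose of IMP at the double-blind treatment phase". It also defines a second baseline, before the first active dose. For lung function, SAP 9.3 uses that one outside the double-blind comparison: "change from baseline of active treatment will be presented for open-label extension phase".

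Protocol 15.5 mentions a mixed-effects model only as a possible further analysis and names no covariates.

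**The concern.** Text and code describe different models. SAP 9.3 is the only section that plans an MMRM and Appendix 15.4 holds the only MMRM code, so the code can refer to nothing else. Neither place says which prevails.

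With a baseline term, FVC and DLCO have a baseline-adjusted treatment comparison. Without it they have none, and with complete data the MMRM estimate at Week 24 equals the difference in mean change that the planned t-test already gives. Both models are defensible, so two legitimate p-values exist for each endpoint and the plan does not fix which is reported. Protocol 15.1 leaves such detail to the SAP, so the SAP is where it should be settled.

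**Working it through.** **1. Term by term**

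| Element | SAP 9.3 text | Appendix 15.4 code |
|---|---|---|
| Response | change from baseline | AnalVar (generic) |
| Treatment | yes | TRT |
| Visit | yes | AVISITN |
| Treatment by visit | yes | TRT*AVISITN |
| Baseline value | not named | BASVAR, continuous, undefined |
| Covariance | unstructured first | type=UN |

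Only the baseline term differs. The code omits the AR(1) and compound symmetry fallbacks, but that is a limit of the illustration and not a contradiction.

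**2. Inputs for the size**

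- From the documents: 55 randomized (SAP 4.1), 1:1 allocation (SAP 4.2), two-sided 0.05 (SAP 4.3).
- Assumed: a 28/27 split; one post-baseline visit; complete data; equal SD at baseline and follow-up; baseline-to-follow-up correlation rho of 0.5 to 0.95; t-test power of 60% or 80%. The documents give no rho, SD, effect size or power, so there is no planned figure to reproduce.

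**3. Gap between the two estimates**

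The chance baseline difference between arms has SD sqrt(1/28 + 1/27) = 0.270 baseline SDs. Adjustment moves the treatment estimate by (1 − rho) times the observed imbalance, so the gap has SD (1 − rho) × 0.270 = 0.135, 0.081, 0.027 and 0.013 SDs at rho 0.5, 0.7, 0.9 and 0.95. Relative to the unadjusted standard error this is sqrt((1 − rho)/2) = 0.50, 0.39, 0.22 and 0.16. When the slope is estimated, simulation gives slightly more: 0.51, 0.40, 0.26 and 0.20.

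**4. Precision**

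Var(adjusted)/Var(unadjusted) = (1 + rho)/2 × 52/51, where 52/51 is the cost of estimating the slope with 55 subjects. The result is 0.765, 0.867, 0.969 and 0.994.

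With a follow-up SD of k times the baseline SD, the ratio is k²(1 − rho²)/(1 + k² − 2k·rho) × 52/51. At k = 1.1 and rho = 0.9 this is 1.21 × 0.19/0.23 × 52/51 = 1.019, a loss of about 2%. The denominator exceeds the numerator by (1 − k·rho)², which cannot be negative. Under this formula the loss therefore never exceeds 1/51, or 2.0%.

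**5. How often the two versions disagree on p<0.05**

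| Setting | rho 0.5 | 0.7 | 0.9 | 0.95 |
|---|---|---|---|---|
| One visit, 60% t-test power | 17.9% | 13.2% | 7.5% | 5.7% |
| Weeks 12 and 24, unstructured REML, 60% power | 18.5% | 13.5% | 7.3% | 5.2% |
| One visit, 80% power | 12.8% | 9.0% | 5.3% | 4.2% |
| One visit, no effect | 4.7% | 3.5% | 2.1% | 1.7% |

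Each cell rests on 20,000 simulated trials. Type I error was 4.6 to 5.3% for both models in the two-visit runs.

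Two variations at about 60% power: if correlations fall with time, disagreement is 10.7% at a Week 24 rho of 0.7 and 4.0% at 0.9. With 20% of Week 24 values missing at random, it is about 16, 11 and 7% at rho 0.5, 0.7 and 0.9 (1,500 trials).

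**The case against.** The best defence is that there is little to reconcile. SAP 9.3 says the model will include three terms, not that it will hold only those; the appendix is a template with placeholder names; and a reader could take the code as the fuller specification. That reading is possible, but no sentence supports it, and the list of fixed effects is the substance of a model specification. What stands is that this is an ambiguity between two reasonable models, not a wrong method.

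It is also fair that the larger disagreement rates need a low rho and an assumed power. For FVC, the wide entry range and the exclusion of subjects whose FVC differs by more than 10% between Visits 1 and 2 point to a higher rho, where disagreement is 5 to 7%. Protocol 7.2.2 describes DLCO as more variable within subjects, so its rho may be lower.

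Three stronger readings might be inferred, and the documents do not support them.

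- **An undisclosed change of plan, because SAP section 13 is silent.** That section is limited to departures from the protocol: "The summary of changes presented below reflects the changes in the planned analysis described in protocol". The protocol names no MMRM covariates, so there was nothing to depart from.
- **Doubt about which baseline is meant.** SAP 4.3 and 9.3 use the baseline of active treatment for the extension phase; the MMRM is confined to the double-blind phase.
- **An error in the other continuous endpoints because they lack baseline adjustment.** For the remaining lung function measures, "change from baseline to each visit in the double-blind treatment phase will be evaluated using a two-sample T-test"; for questionnaires, change and percentage change "in each outcome or questionnaire score will be evaluated using a two-sample T-test". The t-test is the protocol-named method and is valid under randomization. Leaving these endpoints unadjusted is a design choice.

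**Conclusion.** The point holds. SAP 9.3 and Appendix 15.4 give two models for the same analysis, so the reported MMRM result for FVC and DLCO % predicted is not uniquely determined. That follows from the text alone. Reading BASVAR as the baseline value is an inference, but text and code differ whatever it denotes.

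The size rests on the assumptions listed in the working, above all rho. Across rho 0.5 to 0.95 the choice of model would change the significance call in roughly one trial in six down to one in twenty when t-test power is 60%, and in about 5% down to 1.5% when there is no effect. Neither model inflates type I error.

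The consequence is modest. The study is exploratory, with no formal sample size calculation, and the MMRM stands beside a t-test of the same changes. The STS responder analysis and the category-count outcome measures in protocol 7.4 do not use it. A reader might infer that the trial's main efficacy result is in doubt; it is not. The correction should still be made, because it is nearly free and removes a choice that could otherwise be made after seeing the data.

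**What to change.** 1. In SAP 9.3, add the baseline value of the parameter (FVC or DLCO % predicted) to the MMRM covariates.
2. In Appendix 15.4, state that BASVAR is the baseline of overall study, as defined in SAP 4.3, for that parameter.

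This brings the text into line with the existing code and corrects chance baseline imbalance. It usually gains precision, at a worst cost of about 2% in variance in the settings checked. Deleting BASVAR from the code would also remove the conflict, but would give up the adjustment.

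The cost is one phrase and one definition. Baseline is already collected, and no other analysis needs to change.

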9.4. Imaging

9.4.1. HRCT and CXR

Imaging (HRCT and CXR) will be evaluated by the investigator/radiologist and the central reader to determine if the condition is improving, stable, or deteriorating based on a 5-point Likert score: much worse; worse; unchanged; better; much better at week 24 (Visit 8) and week 48 (Visit 11). Data from central reader will be analyzed and listed. Data from investigator/radiologist will only be listed.

Response (improved, stable, and deteriorate) based on the side-by-side comparison of HRCT and CXR is defined as:

Response	Likert Score
Improved	Better; Much Better
Stable	Unchanged
Deteriorate	Much Worse; Worse

The number and percentage of subjects for each Likert score will be summarized for each treatment group by visits, along with number and percentage of subjects with each response of improved, stable, and deteriorate for HRCT and CXR, respectively. The percentage will be calculated based on number of subjects in each treatment group. A bar plot of responses will also be provided.

Pearson's chi-square test (or Fisher's exact test if any expected count is less than 5) will be used to compare the treatment difference between treatment groups for the proportion of subjects with response of improved vs. not improved, and the proportion of subjects with response of not deteriorate vs. deteriorate at week 24 (Visit 8) for HRCT and CXR separately. Subjects who have missing assessments at the visit will be imputed as opposite outcome for the given categorization, i.e. missing response will be imputed as not improved or deteriorate, as applicable.

A secondary analysis will then be performed by only including subjects with assessments evaluated. The percentage of subjects in each category will be calculated based on number of subjects with assessments in each treatment group at each scheduled visit (Visit 8 and Visit 11).

9.4.2. Scadding Score

The number and percentage of subjects for each Scadding score (Stage 0, Stage I; Stage II; Stage III; and Stage IV) will be summarized at week 24 (Visit 8) and week 48 (Visit 11) by treatment group. Pearson's chi-square test (or Fisher's exact test if any expected count is less than 5) will be used to compare the treatment difference between treatment groups.

The Scadding score will be converted to numeric score in the following manner:

0 - Stage 0

1 - Stage I

2 - Stage II

3 - Stage III

4 - Stage IV

Descriptive statistics of observed, change from baseline and percentage change from baseline values will be presented by treatment group at week 24 (Visit 8) and week 48 (Visit 11) for the Scadding score. Baseline of active treatment, change from baseline and percentage change from baseline values will be presented as well for week 48 (Visit 11). Note that the percentage change will not be calculated for subjects with Scadding score stage 0 at baseline.

The treatment difference between Acthar and placebo for both change from baseline and percentage change from baseline to week 24 (Visit 8) in Scadding score will be evaluated using a Wilcoxon rank sum test.

A listing will be provided for the imaging data and Scadding score by subject and visit.

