7.2.3. Imaging (HRCT; CXR)

[figure not shown]
Although granulomas are microscopic structures, sarcoidosis granulomas have a proclivity to coalesce into macroscopic nodular conglomerations that are capable of being detected with plain radiographic or HRCT radiographic techniques. HRCT reveals more sarcoidosis lung involvement than the CXR including, identifying more parenchymal and mediastinal/hilar disease as well as parenchymal details to reliably differentiate from other diffuse lung diseases. HRCT findings have been correlated with lung pathology and have been proposed as a biomarker of disease activity.

The intriguing observations of chest radiographs in sarcoidosis published by Scadding in 1961 ([Scadding, 1961](#); [Attachment 11](#)) are still considered the gold standard because of the limited use of radiation and its association with resolution or progression of the disease although these stages do not necessarily progress or regress from one to another. However, interobserver variability and lack of association with functional clinical parameters (eg, PFT, 6MWT) are limiting factors ([Korsten et al., 2016](#); [Chopra et al., 2016](#)).

Imaging will be evaluated by the investigator/ radiologist and the central reader to determine if the condition is improving, stable, or deteriorating based on a 5-point Likert score: much worse; worse; unchanged; better; much better.

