- Clinical laboratory tests. Samples will be collected from subjects who have been fasted for at least 12 hours (drinking water is allowed). The following tests will be conducted:
 - Complete blood count.
 - Clinical chemistry (including liver function tests).
 - HbA1C.
 - Lipid profile.
 - 25-Hydroxy vitamin D and 1, 25-dihydroxy vitamin D, and parathyroid hormone.
 - C-reactive protein.
 - Thyroid stimulating hormone, thyroxine T3 and T4.
 - Hepatitis serology- Hepatitis B surface antigen, Hepatitis B core antibody, hepatitis C virus antibody, hepatitis C polymerase chain reaction for subjects positive for hepatitis C antibody only.
 - Biomarkers (including RNA and DNA, if genetic ICF signed).
 - Serum human chorionic gonadotropin hormone (females of child bearing potential only).
 - Urine analysis (local laboratory).
- Tuberculosis testing (tested by IGRA).
- PFT.
- CXR and HRCT should be performed within 28 days of Day -1. The CXR reading will also include Scadding scoring ([Attachment 11](#)).
- AEs (collected from the time of signature of the ICF).

- Contact IXRS to register subject.
- Schedule next visit and remind subjects to arrive in fasting condition for Visit 2 (drinking water is permitted).

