4.1. Sample Size

Formal sample size calculations were not performed. The sample size is based on recent literature of comparative studies ([Gibson et al., 1996](#); [Baughman et al., 2006](#); [Judson, 2014](#)) in sarcoidosis. There are 55 subjects randomized to this study.

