4.2. Randomization, Stratification, and Blinding

An interactive telephone/web response system will be used to allocate eligible subjects to each treatment group. Subjects will be randomized according to computer-generated allocation scheme to receive either Acthar Gel 1 mL (80 U) or placebo 1 mL administered twice a week in a 1:1 ratio. Both investigators and the subjects will be blinded to the treatment assignment. A block randomization will be performed.

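### The chi-square/Fisher test of Week 24 Scadding stage (SAP 9.4.2) ignores Screening stage and stage order, so it adds a valid but weak third p-value beside the planned Wilcoxon tests

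*SAP*

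**What the plan says.** **The test.** SAP 9.4.2 begins: "The number and percentage of subjects for each Scadding score (Stage 0, Stage I; Stage II; Stage III; and Stage IV) will be summarized at" Weeks 24 and 48, by treatment group. On the comparison of the two arms it continues: "Pearson's chi-square test (or Fisher's exact test if any expected count is less than 5) will be used to compare the treatment difference between treatment" … No baseline term appears, and the five stages are treated as unordered. The opening of SAP section 9 makes open-label efficacy descriptive only, so the between-arm test applies to Week 24.

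**The baseline value exists.** Protocol 11.1 says of the Screening film: "The CXR reading will also include Scadding scoring". Under the baseline definition in SAP 4.3, that reading is the baseline.

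**Other Scadding tests in the same section.** The SAP codes the stages 0 to 4 and applies Wilcoxon rank sum tests to change and to percentage change from baseline to Week 24. Percentage change is not calculated for subjects at stage 0 at baseline. The listed endpoint (Protocol 7.3, SAP 3.2.1) is percentage change in Scadding score. The section does not say which of the three p-values is to be interpreted.

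**Setting.** Tests "will be 2-sided with a significance level of 0.05" (SAP 4.3). SAP 4.1 states "Formal sample size calculations were not performed" and "There are 55 subjects randomized to this study". SAP 4.2 describes 1:1 block randomization and names no stratification factor.

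**The concern.** A subject's stage at Week 24 depends partly on the stage at entry. A test on Week 24 stage alone leaves that between-subject variation in the comparison, although the Screening reading could remove it. It also spreads the comparison over every possible difference between five unordered categories ((5 - 1) × (2 - 1) = 4 degrees of freedom for chi-square) rather than looking for a shift toward better stages.

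What is at stake is interpretation. A null stage result beside a positive result on change could be read as contradiction when it mainly reflects low power. A significant stage result may reflect a difference already present at Screening. This is a supportive endpoint in an exploratory study, so the consequence is small.

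**Working it through.** **1. No plan figure to reproduce.** The SAP states no power or effect size for this test. The inputs from the documents are 55 subjects, 1:1 allocation (taken as 28 v 27), five stages and two-sided 0.05. Baseline stage mix and stage movement are assumptions, because the documents give neither. All simulations assume no dropout.

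**2. Which branch of the test applies.** In the smaller arm, the expected count for a stage held by c of the 55 subjects is 27c/55. This is below 5 when c < 5 × 55/27 = 10.2, that is, when c is 10 or fewer. If all five stages occur, chi-square applies only if every stage holds exactly 11 subjects (5 × 11 = 55). Fisher's exact test is therefore the test that would almost always be run. In the simulations below it was triggered in at least 99% of runs at 55 subjects.

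**3. The SAP's own tests, simulated.** The chi-square/Fisher rule on Week 24 stage was compared with the Wilcoxon rank sum test on change in stage, with 2000 trials per scenario. Three baseline mixes for stages 0 to IV were assumed: 20% each; 8/17/40/20/15%; and 3/7/35/30/25%. On placebo, 5% improve one stage; in both arms, 5% worsen one stage. Ranges are over the three mixes.

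| Assigned to improve on Acthar (placebo 5%) | Chi-square/Fisher on Week 24 stage | Wilcoxon on change |
|---|---|---|
| 5% (no effect) | 4.6-5.1% | 4.3-5.2% |
| 20% | 5-7% | 23-28% |
| 30% | 7-9% | 46-62% |
| 40% | 8-13% | 69-85% |
| 50% | 11-22% | 86-95% |

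The simulation standard error is about 0.5 points near 5% (√(0.05 × 0.95/2000) = 0.0049) and about 1.1 points near 50% (√(0.5 × 0.5/2000) = 0.011). At 100 subjects (300 trials per scenario) the stage test reaches only 8-15% with 30% improving and 12-26% with 40%.

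**4. A test stratified by Screening stage.** With baseline mix 5/15/40/25/15%, the same 5% movement each way and 3000 trials, using chi-square for the stage test:

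| Extra improving on Acthar | Chi-square on Week 24 stage | Stratified mean-score test | Wilcoxon on change |
|---|---|---|---|
| 0 | 3.4% | 4.3% | 5.4% |
| 15 points | 5.0% | 23.7% | 24.6% |
| 25 points | 7.6% | 51.3% | 54.6% |
| 35 points | 11.3% | 74.3% | 79.3% |

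Wilcoxon on change exceeds the stratified test by 0.9, 3.3 and 5.0 points in the three effect rows.

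**5. Sensitivity to the assumed movement.** For the same three effects, with 2000 trials each and chi-square for the stage test:
- 15% improving and 15% worsening on placebo: stage test 5%, 9%, 12%; stratified 14%, 30%, 49%.
- 25% each way: stage test 6%, 8%, 11%; stratified 11%, 22%, 37%.

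A further run over three baseline mixes at two movement levels, again with chi-square as a proxy for Fisher, gave 4-13% for the stage test and 13-78% for the stratified test.

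**6. How far Screening drives a chance finding.** With no effect and 5% movement each way, 47-59% of significant Week 24 stage results (chi-square/Fisher rule, 55 subjects) came from trials where the arms also differed at Screening at p < 0.05. With the looser criterion p < 0.10 and chi-square, the share was 73%, 44% and 34% as movement each way rose from 5% to 15% to 25%. It falls steadily as stages become more mobile.

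**The case against.** The strongest reply is that the plan already uses baseline. SAP 9.4.2 tests change and percentage change, the latter being the listed endpoint, and SAP 9.4.1 separately tests the side-by-side chest X-ray reading as improved or not and deteriorated or not. This stands. A reader might infer that Scadding is analysed without its baseline; the documents do not support that. Nor would a stratified test add power to the Scadding question, since the planned Wilcoxon test on change does as well or slightly better in nearly every scenario.

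A second reply is that the test is valid under randomization. This also stands. Rejection under no effect is about 5%, and chance imbalance at Screening is part of that 5%. A reader might infer bias, or that the p-value mostly measures baseline imbalance. The first is wrong, and the second depends on movement rates that the documents do not give.

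A third reply is that the premise of stable stages is not in the protocol. Protocol 7.2.3 says "these stages do not necessarily progress or regress from one to another", which concerns movement in sequence and says nothing about how fast stage changes over 24 weeks. That is correct. One could even argue from it for an unordered test as a companion to the Wilcoxon. But the low power does not need near-immobile stages: it persists with 25% assigned to move each way on placebo.

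Finally, chi-square is the protocol's general method for categorical endpoints (Protocol 15.5), and the imaging component of the Sarcoidosis Treatment Score is HRCT, so nothing decisive rests on this p-value. That limits the severity; it does not make the test informative.

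**Conclusion.** The point holds for one test only, and its severity is low. The chi-square/Fisher comparison of Week 24 stage discards the Screening stage and the stage order. With 55 subjects its power is about 4-13%, against about 13-78% for a test stratified by Screening stage. These ranges assume one-stage moves, 5-15% each way on placebo, and an extra 15-35 points improving on Acthar. Under a larger effect (50% improving against 5%) the stage test still reaches only 11-22%. The exact figures depend on the assumed baseline mix and movement; the ranking of the two tests was the same in every effect scenario tried.

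The test is inefficient, not invalid. Because the Wilcoxon test on change is already planned, the loss is in clarity: a third treatment p-value that carries little information and has no stated place beside the other two.

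**What to change.** In SAP 9.4.2, present the categorical Week 24 result as a shift table from Screening to Week 24 by arm. The SAP already plans shift tables for hematology and chemistry (10.2.1, 10.2.2). Then take one of two routes:

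- Make the table descriptive, drop its p-value, and name the planned Wilcoxon test on change as the Scadding analysis to interpret. State how this relates to the listed percentage-change endpoint, which excludes subjects at stage 0 at baseline.
- Or replace the chi-square/Fisher test by an ordinal test stratified by Screening stage, such as van Elteren or a Mantel-Haenszel mean-score test.

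The cost is a few sentences of SAP text and one changed table, with no new data. The downside of the second route is thin strata: at an assumed 5% in stage 0, only about 55 × 0.05 = 2.75 subjects start there. Rules for pooling adjacent Screening stages should therefore be prespecified.
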